6.12.1.2.2. Maintenance Dosing Period Relapse Population

The duration of exposure on re-treatment will be calculated as:

$$\begin{aligned} & \textit{Duration of re-treatment exposure (days)} \\ &= \textit{Date of last visit (scheduled or unscheduled) in Period 3} \\ & \quad - \textit{Date of first dose following relapse} + 1 \end{aligned}$$

The number and percentage of patients in each of the following categories will be summarized: >0 days, ≥7 days, ≥14 days, ≥30 days, ≥60 days, ≥90 days, ≥120 days, ≥183 days, and ≥365 days.

Note that patients may be included in more than one category. The number and percentage of patients falling into the following subcategories will also be summarized: >0 to <7 days, ≥7 to <14 days, ≥14 to <30 days, ≥30 to <60 days, ≥60 to <90 days, ≥90 to <120 days, ≥120 to <183 days, ≥183 to <365 days, and ≥365 days.

The summaries will also include the following information:

- Total exposure in patient years, calculated as:

$$\text{Re-treatment exposure in patient years} = \frac{\text{Sum of duration of re-treatment exposure for all patients in treatment group}}{365.25}$$

- Mean and median total dose (in mg). The total dose (in mg) taken during Period 3 following relapse will be calculated as follows:

$$\text{Total Period 3 relapse dose} = \text{Total number of active injections received in Period 3 following relapse} \times 80$$

Note that the total number of injections received will be calculated using the response to the question ‘Was dose administered?’ on the *Exposure as Collected* eCRF page and the actual dose description from IWRS study drug dispense dataset.

6.12.2. Adverse Events

Adverse events (AEs) will be classified based upon the latest version of the MedDRA. Any condition starting on or after the date of informed consent will be considered an AE. Any preexisting condition which worsens in severity on or after the date of informed consent will be considered and recorded as an AE on the *Adverse Event (AE)* eCRF page from the date of worsening onwards.

A treatment-emergent adverse event (TEAE) is defined as an event that first occurred or worsened in severity after baseline and on or prior to the date of the last visit within the defined treatment period. Both the date/time of the event and the date/time of the dose (that is, injection) are considered when determining TEAEs. Treatment-emergent AEs will be assigned to the study period to which it’s considered treatment-emergent:

- The MedDRA lowest level term (LLT) will be used when classifying AEs as treatment-emergent.
- The maximum severity recorded for each LLT prior to the first dose date/time in the treatment period will be used as the pre-treatment severity for that LLT. If an event during the baseline period has missing severity, and the event persists during the treatment period, then it will be considered as treatment-emergent, regardless of the post-baseline level of severity. Events with a missing severity during the treatment period will be considered treatment-emergent.
- AEs with a particular LLT will be classified as treatment-emergent if they first start on or after the first dose date/time in the treatment period (i.e., a patient has no preexisting conditions with that lowest level term), or if the severity is greater than the pre-treatment severity for that lowest level term. If a partial AE start date/time is present, the date/time

will be compared as far as possible to the treatment start date/time in order to determine whether the event is treatment-emergent or not. If there is any doubt, the event will be flagged as treatment-emergent.

A follow-up emergent adverse event (FEAE) is defined as an event that first occurred or worsened in severity after the date of Visit 19 (that is, Week 60) or the ETV:

- The MedDRA LLT will be used when classifying AEs as follow-up emergent.
- For AEs that are ongoing at the date of Visit 19 or ETV, the maximum severity recorded for each LLT on or prior to the date of Visit 19 or ETV will be used as the follow-up baseline severity for that LLT.

Adverse events and TEAEs will be summarized for the following time periods and analysis populations:

- Period 2 (Safety Population)
- Period 3 (Maintenance Dosing Period Primary/Secondary/Relapse Population)
- Period 4 (Follow-up Population)

An overall summary of AEs including the number and percentage of patients who experienced TEAE, TEAE by maximum severity, death, SAE, TEAE possibly related to study treatment, discontinuations from the treatment due to an AE, and TEAEs of special interest will be performed for Periods 2 (Safety Population) and 3 (Maintenance Dosing Period Primary/Secondary/Relapse Population).

The following summaries/analyses will be performed for Periods 2 (Safety Population) and 3 (Maintenance Dosing Period Primary Population), unless noted otherwise:

- TEAE by SOC and PT.
- TEAE by PT.
- TEAE by maximum severity, SOC, and PT.

Follow-up emergent AEs will be summarized for the Follow-Up Population in Period 4:

- FEAE by PT.

In general, for all AE-related summaries, the number and percentage of patients experiencing the events will be presented by treatment group. In general, events will be ordered by decreasing frequency in the total ixekizumab group, followed in the order of ixekizumab Q2W, ixekizumab Q4W, and placebo (when applicable) group, within SOC and/or PT for sorting. For events that are gender-specific (as defined by MedDRA), the denominator and computation of the percentage will include only patients from the given gender.

A by-patient listing of all AEs for safety population will be provided.

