Efficacy, health outcomes, and safety analyses for Period 3 will also be conducted on the Maintenance Dosing Period Secondary population, defined as the ixekizumab patients who were not re-randomized at Week 12 or patients who were randomized to placebo at Week 0, who received at least 1 dose of study treatment during the maintenance dosing period. Patients will be analyzed according to the treatment to which they were assigned upon entry into Period 3.

Safety analyses for Period 4 (Post-Treatment Follow-up Period) will be conducted on the follow-up population, defined as all randomized patients who received at least 1 dose of study treatment and have entered the post-treatment follow-up period. Patients will be analyzed according to the treatment they actually received prior to entering Period 4.

Additional analysis populations will be described in the SAP.

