#### **12.2.8.1. Adverse Events**

A TEAE is defined as an event that first occurred or worsened in severity after baseline and on or prior to the date of the last visit within the treatment period.

Treatment-emergent adverse events (TEAEs), SAEs including deaths, AEs that led to investigational product discontinuation, and AEs by maximum severity and relationship to investigational product will be summarized by the MedDRA system organ class (SOC) and PT. For events that are gender specific, the denominator and computation of the percentage will include only patients from the given gender.

MedDRA groupings of PTs will be used to investigate AESIs. Adverse events of special interest (AESIs) may also be presented by severity.

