5.3. Determination of Sample Size

The total sample size for the study is 420 patients randomized at a 2:2:1 ratio in the blinded Induction Dosing Period to 80 mg Q2W, 80 mg Q4W, and placebo, respectively. In order to account for multiple testing for the 2 ixekizumab groups, a 2-sided Fisher's exact test at the 0.025 level is assumed. Assuming the response rates for both sPGA (0,1) and PASI 75 at Week 12 (Visit 7) are 75% for each ixekizumab treatment group and 5% for the placebo group, 168 patients in 80 mg Q2W or 80 mg Q4W versus 84 patients in placebo group will provide >99% power to test the superiority of each ixekizumab dose regimen to placebo for sPGA (0,1) and for PASI 75. These assumptions are based on the integrated results from the pivotal Phase 3 Studies RHAZ, RHBA, and RHBC.

Assuming 70% of the ixekizumab patients are re-randomized in the Maintenance Dosing Period at Week 12 (Visit 7) at a 2:1 ratio to 80 mg Q4W or placebo, approximately 78 patients will be included in 80 mg Q4W group and 39 patients in placebo group. This sample size will:

- provide >99% power to test the difference in the proportion of patients maintaining sPGA (0, 1) from Week 12 (Visit 7) after re-randomization at start of Maintenance Dosing Period to Week 60 (Visit 19) in the Maintenance Dosing Period Primary population between the ixekizumab dosing interval and placebo within the original treatment group, assuming the proportions of patients maintaining sPGA (0, 1) are 70% for 80 mg Q4W and 10% for placebo within each original treatment group (Visit 19). A 2-sided Fisher's exact test at the 0.025 significance level is assumed.
- provide >99% power to test the difference in the proportion of patients maintaining a PASI 75 from Week 12 (Visit 7) after re-randomization at start of Maintenance Dosing Period to Week 60 (Visit 19) in the Maintenance Dosing Period Primary population

between the ixekizumab dosing interval and placebo within each original treatment group, assuming the proportions of patients maintaining a PASI 75 are 70% for 80 mg Q4W and 10% for placebo within each original treatment group. A 2-sided Fisher's exact test at the 0.025 significance level is assumed.

6. A Priori Statistical Methods

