6.12.3. Deaths, Other Serious Adverse Events, and Other Notable Adverse Events

By-patient listings of deaths, SAEs, and AEs leading to discontinuation (including death) will be provided, respectively.

All deaths will be included, regardless of the investigator's or the sponsor's judgment about causality, including:

- any deaths occurring during participation in the study in the database for which data are being presented
- any deaths occurring after a patient leaves (is discontinued from or completed) the study in the database for which data are being presented if the death:
 - is the result of a process initiated during the study, regardless of when it actually occurred, or
 - occurs during the Period 4 after discontinuation of study drug.

An SAE is any AE that results in one of the following outcomes: death, life-threatening, initial or prolonged hospitalization, disability or permanent damage, congenital anomaly or birth defect, or any other serious/important medical events.

The following summary tables will be provided for Periods 2 (Safety Population) and 3 (Maintenance Dosing Period Primary Population):

- SAEs by PT
- AEs that lead to treatment discontinuation (including death) by PT.

A follow-up emergent serious adverse event (FESAE) is defined as an SAE that first occurred or worsened in severity after the date of Visit 19 (that is, Week 60) or the ETV.

The following summary tables will be provided for the Follow-Up Population in Period 4:

- FESAE by PT
- FEAEs that lead to treatment discontinuation (including death) by PT.

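### The SAP's general Period 3 by-term adverse event tables cover only the Primary Population before relapse, leaving out patients who carry roughly half to two thirds of planned Period 3 ixekizumab exposure

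*SAP*

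**What the plan says.** SAP 6.12.2 lists three tables: treatment-emergent adverse events (TEAEs) by system organ class (SOC) and preferred term (PT), by PT alone, and by maximum severity with SOC and PT. It introduces them with "The following summaries/analyses will be performed for Periods 2 (Safety Population) and 3 (Maintenance Dosing Period Primary Population), unless noted otherwise". Nothing in the section then notes otherwise for Period 3. SAP 6.12.2.1 applies the same limit to common TEAEs by PT. SAP 6.12.3 does so for serious adverse events (SAEs) by PT and for adverse events leading to treatment discontinuation by PT: "The following summary tables will be provided for Periods 2 (Safety Population) and 3 (Maintenance Dosing Period Primary Population)". SAP 6.1.1 restricts what is shown for the Primary Population to information before relapse.

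For the Secondary and Relapse Populations, the same sections provide an overall summary and by-patient listings. The overall summary counts patients with any TEAE, TEAEs by maximum severity, deaths, SAEs, related TEAEs, discontinuations and events of special interest. SAP 6.1.3.2, 6.1.3.3 and 6.12 promise incidence summaries or treatment-emergent summaries for these populations but give no by-term layout.

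Protocol 12.2.8.1 says that TEAEs, SAEs and events leading to discontinuation "will be summarized by the MedDRA system organ class (SOC) and PT", and names no population. Protocol 12.2.1.3 adds: "Efficacy, health outcomes, and safety analyses for Period 3 will also be conducted on the Maintenance Dosing Period Secondary population".

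**The concern.** The limit looks deliberate. Where the SAP wants other populations included, it names them: the overall event summary in 6.12.2 covers all three Period 3 populations, and 6.7.2 adds the Secondary and Relapse Populations for concomitant therapy. Patients in off-treatment follow-up get follow-up-emergent events, serious and otherwise, by PT. Patients on ixekizumab in the Secondary and Relapse Populations get no such table in the same sections.

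Three groups are affected:
- ixekizumab non-responders at Week 12 who stay on ixekizumab;
- placebo non-responders who start ixekizumab at Week 12;
- Week 12 responders who relapse and receive ixekizumab afterwards, including those re-exposed after withdrawal to placebo.

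Evaluating the safety of the maintenance regimen is a stated aim of Period 3 (Protocol 7.1, SAP 5.1). For these groups, a reader of 6.12.2 and 6.12.3 output would see how many patients had any event or any serious event. To learn which events, and how often in each group, the reader would have to count from listings.

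**Working it through.** **Inputs, all from SAP 5.3 unless stated**
- Allocation: "The total sample size for the study is 420 patients randomized at a 2:2:1 ratio", so 168, 168 and 84 patients.
- Re-randomisation: "Assuming 70% of the ixekizumab patients are re-randomized in the Maintenance Dosing Period", at 2:1.
- Week 12 response: "75% for each ixekizumab treatment group and 5% for the placebo group".
- Period 3 runs from Week 12 to Week 60, which is 48 weeks (SAP 6.1.3).

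**The plan's own figure.** 168 × 0.70 = 117.6 re-randomised per induction arm. Split 2:1, this is 78.4 and 39.2, which reproduces "approximately 78 patients will be included in 80 mg Q4W group and 39 patients in placebo group". Over both induction arms: 2 × 78 = 156 on ixekizumab and 2 × 39 = 78 on placebo.

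**Patients outside the Primary Population who take ixekizumab from Week 12**
- Ixekizumab patients not re-randomised: 336 × 0.30 = 100.8.
- Placebo non-responders: 84 × 0.95 = 79.8, about 80. If 10% leave during induction, 79.8 × 0.90 = 71.8, about 72.
- Total without dropout: 180.6.

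**Secondary Population alone, no relapse time counted:** 180.6 / (180.6 + 156) = 54%.

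**Adding time after relapse.** The documents give neither relapse rates nor relapse timing, so these are assumptions. Let *r* be the proportion relapsing on ixekizumab, at mean week *t* of Period 3. Let *p* be the proportion relapsing on re-randomised placebo, at mean week *s*. In patient-weeks on ixekizumab:
- Primary, before relapse = 156 × [(1 − r) × 48 + r × t]
- Secondary = (ixekizumab non-responders + placebo non-responders) × 48
- After relapse = 78 × p × (48 − s) + 156 × r × (48 − t)
- Share outside = (Secondary + After relapse) / total

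| Case | Primary | Secondary | After relapse | Share outside |
|---|---|---|---|---|
| Middle: p = 0.8, s = 20; r = 0.1, t = 24 | 7,113.6 | 8,668.8 | 2,121.6 | 60% |
| Late placebo relapse: p = 0.7, s = 28; r = 0 | 7,488.0 | 8,668.8 | 1,092.0 | 57% |
| Early relapse: p = 0.9, s = 12; r = 0.3, t = 24 | 6,364.8 | 8,668.8 | 3,650.4 | 66% |
| Low: 20% ixekizumab non-responders (67.2), 72 placebo; p = 0.7, s = 28; r = 0 | 7,488.0 | 6,681.6 | 1,092.0 | 51% |
| High: p = 0.9, s = 8; r = 0.3, t = 16 | 5,990.4 | 8,668.8 | 4,305.6 | 68% |

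In the low case the Secondary Population alone gives 6,681.6 / 14,169.6 = 47%, so it is the time after relapse that brings the share above half. In the middle case the placebo non-responders' first exposure alone is 79.8 × 48 / 17,904 = 21% of the total.

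**The case against.** **Other output exists.** A reader might infer that these patients get no by-term output at all. The SAP does not support that. Section 6.16 plans SAEs and other TEAEs by treatment group and PT, with numbers at risk, and names no population. In Table RHBH.6.8 the Period 3 restriction is mostly attached to the Fisher test, so the by-PT summaries of special topics may extend to all three populations; the hepatic shift entry limits the summary itself, which suggests the two wordings differ on purpose. This stands, but it does not close the gap. Section 6.16 omits discontinuation events, SOC and severity, and does not commit to these groups. Table RHBH.6.8 covers special topics only, and its all-infections entry lists no table of TEAEs by PT.

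**No contradiction or clear breach.** A reader might also infer that the SAP contradicts itself or breaks the protocol. Protocol 12.2.8.1 names no period or population, Protocol 12.2.1.2 leaves details on the Secondary Population to the SAP, and Protocol 12.2.8 puts the main safety focus on Period 2. Overall counts are a form of safety analysis. The fair description is that the general promises in 6.1.3.2, 6.1.3.3 and 6.12 are not carried into the by-term table lists.

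**The share is assumption-driven.** SAP 5.3 gives rates of maintaining sPGA (0,1), 70% and 10%. Their complements are not relapse rates: a patient at sPGA 2, or with missing data, fails maintenance without meeting the relapse definition of sPGA 3 or more. Some dropout is planned, since the protocol synopsis expects 336 of 420 to complete. The 75% response rate would leave at most 25% of 336, or 84, ixekizumab non-responders; the Secondary Population alone is then (84 + 80) / (84 + 80 + 156) = 51%. The Week 24 discontinuation criterion in Protocol 8.3.1.1 would shorten some non-responders' exposure further, and the table above does not model it. All of this stands, and it is why a range is given.

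**Conclusion.** The point holds for the general tables in 6.12.2, 6.12.2.1 and 6.12.3. Their Period 3 by-term output is expressly limited to the Primary Population before relapse, while the protocol's corresponding commitments carry no such limit. The patients left out account for roughly half to two thirds (about 51% to 68%) of planned Period 3 ixekizumab exposure, including the first exposure of about 80 placebo patients. The patient numbers follow from SAP 5.3. The range also rests on assumed relapse proportions, relapse timing and induction dropout; it is not a bound and should not be quoted as a planned figure. No data are lost, because counts and listings cover everyone. It is a reporting gap worth closing before the tables are produced.

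**What to change.** In SAP 6.12.2 and 6.12.3, extend four Period 3 tables to the Secondary and Relapse Populations: TEAEs by SOC and PT, TEAEs by PT, SAEs by PT, and events leading to treatment discontinuation by PT. Keep them descriptive, as Table RHBH.6.1 specifies no comparison for either population. Use that table's groups, with the pooled column Total IXE for the Secondary Population and Total for the Relapse Population, which has no Total IXE group.

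State that Secondary Population data for placebo responders stop at relapse. These patients (84 × 0.05, about 4) belong to both populations, and without a cut-off their later events would be counted twice. SAP 6.12.1.2.1 already stops maintenance exposure at relapse, so numerators and exposure would match.

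The cost is a few more descriptive tables from programs already needed for the Primary Population, with no new data and no new tests.

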6.12.2.1. Common Adverse Events

Common TEAEs are those TEAEs that occurred in $\geq 1\%$ before rounding of total ixekizumab treated patients.

The following summaries will be provided for common TEAEs for Periods 2 (Safety Population) and 3 (Maintenance Dosing Period Primary Population):

- Common TEAEs by PT

6.12.3. Deaths, Other Serious Adverse Events, and Other Notable Adverse Events

By-patient listings of deaths, SAEs, and AEs leading to discontinuation (including death) will be provided, respectively.

All deaths will be included, regardless of the investigator's or the sponsor's judgment about causality, including:

- any deaths occurring during participation in the study in the database for which data are being presented
- any deaths occurring after a patient leaves (is discontinued from or completed) the study in the database for which data are being presented if the death:
 - is the result of a process initiated during the study, regardless of when it actually occurred, or
 - occurs during the Period 4 after discontinuation of study drug.

An SAE is any AE that results in one of the following outcomes: death, life-threatening, initial or prolonged hospitalization, disability or permanent damage, congenital anomaly or birth defect, or any other serious/important medical events.

The following summary tables will be provided for Periods 2 (Safety Population) and 3 (Maintenance Dosing Period Primary Population):

- SAEs by PT
- AEs that lead to treatment discontinuation (including death) by PT.

A follow-up emergent serious adverse event (FESAE) is defined as an SAE that first occurred or worsened in severity after the date of Visit 19 (that is, Week 60) or the ETV.

The following summary tables will be provided for the Follow-Up Population in Period 4:

- FESAE by PT
- FEAEs that lead to treatment discontinuation (including death) by PT.

6.12.3.1. Special Safety Topics including Adverse Events of Special Interest

Safety information on special topics including AEs of special interest (AESI) will be presented by treatment group and by study period. [Table RHBH. 6.8.](#) provides the definitions/derivations and analyses methods (including analyses, summaries and by-patient listings) of special safety topics including AESIs.

Potential AESIs will be identified by a standardized MedDRA query (SMQ) or a Lilly-defined MedDRA PT listing. Preferred terms within an SMQ will be classified as broad and narrow. In the Lilly-defined MedDRA PT listings, Lilly has provided the broad and narrow classification.

The Lilly-defined broad terms are for a more sensitive search of potential events of interest and the Lilly-defined narrow terms are for a more specific search. Therefore, the summaries will include the classifications of broad term and narrow term.

In the event that the listing of terms or analysis changes for a special safety topic, it will be documented in the program safety analysis plan (PSAP) which will supersede this document; it will not warrant an amendment to the individual study SAP. For final analysis, the most current version of PSAP will be used, including PSAP released after SAP finalization but before database lock.

In general, AESI summary will not be provided for Follow-up Population during Period 4 except hepatic laboratory tests.

Table RHBH. 6.8. Definitions and Analyses of Special Safety Topics including Adverse Events of Special Interest

Special Safety Topic	Definition / Derivation	Analysis / Summary / Listing
Hepatic	
Hepatic AE analysis will include events that are potentially drug-related hepatic disorders by using the Medical Dictionary for Regulatory Activities (MedDRA) PTs contained in any of the following standardized MedDRA query (SMQ) or sub-SMQ as defined in MedDRA:
 
 • Broad and narrow terms in the Liver related investigations, signs and symptoms (20000008) • Broad and narrow terms in the Cholestasis and jaundice of hepatic origin (20000009) • Broad and narrow terms in the Hepatitis, non-infectious (20000010) • Broad and narrow terms in the Hepatic failure, fibrosis and cirrhosis and other liver damage (20000013) • Narrow terms in the Liver-related coagulation and bleeding disturbances (20000015) 	
Period 2 (Fisher’s exact test), Period 3 (Fisher’s exact test for Maintenance Dosing Period Primary Population): TEAE by PT within SMQ or sub-SMQ
 
Listing: TEAE

	
Elevations in hepatic laboratory tests (ALT, AST, ALP, total bilirubin) using performing lab reference ranges are defined as:
 
 • Include scheduled visits, unscheduled visits, and repeat measurements. • Alanine aminotransferase (ALT) or aspartate aminotransferase (AST): maximum post-baseline measurement ≥ 3 times ($3\times$), 5 times ($5\times$), 10 times ($10\times$), and 20 times ($20\times$) the performing lab upper limit of normal (ULN) for all patients with a post-baseline value. 
 ○ The analysis of $3\times$ ULN will contain 4 subsets: patients whose non-missing maximum baseline value is $\leq 1\times$ ULN, $>1\times$ ULN to $<3\times$ ULN, $\geq 3\times$ ULN, or missing. ○ The analysis of $5\times$ ULN will be contain 5 subsets: patients whose non-missing maximum baseline value is $\leq 1\times$ ULN, $>1\times$ ULN to $<3\times$ ULN, $\geq 3\times$ ULN to $<5\times$ ULN, $\geq 5\times$ ULN, or missing. ○ The analysis of $10\times$ ULN will contain 6 subsets: patients whose non-missing maximum baseline value is $\leq 1\times$ ULN, $>1\times$ULN to $<3\times$ ULN, $\geq 3\times$ ULN to $<5\times$ ULN, $\geq 5\times$ ULN to $<10\times$ ULN, $\geq 10\times$ ULN, or missing. ○ The analysis of $20\times$ ULN will contain 7 subsets: patients whose non-missing maximum baseline value is $\leq 1\times$ULN, $>1\times$ULN to $<3\times$ ULN, $\geq 3\times$ ULN to $<5\times$ ULN, $\geq 5\times$ ULN to $<10\times$ ULN, $\geq 10\times$ ULN to $<20\times$ ULN, $\geq 20\times$ ULN, or missing. • Total bilirubin: maximum post-baseline measurement ≥ 1.5 times ($1.5\times$), and ≥ 2 times ($2\times$) the performing lab ULN for all patients with a post-baseline value 
 ○ The analysis of $1.5\times$ ULN will contain 4 subsets: patients whose non-missing 	
Period 2 (Fisher’s exact test), Period 3 (Fisher’s exact test for Maintenance Dosing Period Primary Population), Period 4 (Summary): Elevations in hepatic laboratory tests: maximum baseline category to abnormal maximum post-baseline category

Special Safety Topic	Definition / Derivation	Analysis / Summary / Listing
	
maximum baseline value is $\leq 1 \times \text{ULN}$, $> 1 \times \text{ULN}$ to $< 1.5 \times \text{ULN}$, $\geq 1.5 \times \text{ULN}$, or missing.
 
 ○ The analysis of $2 \times \text{ULN}$ will contain 5 subsets: patients whose non-missing maximum baseline value is $\leq 1 \times \text{ULN}$, $> 1 \times \text{ULN}$ to $< 1.5 \times \text{ULN}$, $\geq 1.5 \times \text{ULN}$ to $< 2 \times \text{ULN}$, $\geq 2 \times \text{ULN}$, or missing. ● Alkaline phosphatase (ALP): maximum post-baseline measurement > 1.5 times ($1.5 \times$) the performing lab ULN for all patients with a post-baseline value, and divided into 4 subsets: patients whose non-missing maximum baseline value is $\leq 1 \times \text{ULN}$, $> 1 \times \text{ULN}$ to $\leq 1.5 \times \text{ULN}$, $> 1.5 \times \text{ULN}$, or missing. 	
	
Shift for ALT, AST, ALP and total bilirubin from maximum baseline to maximum post-baseline will be produced with the requirements using performing lab reference ranges:
 
 ● Include scheduled visits, unscheduled visits, and repeat measurements. ● Use the maximum non-missing value in the baseline period. ● Use the maximum non-missing post-baseline value within each study period. ● Categories are: 
 ○ ALT: $\leq 1 \times \text{ULN}$, > 1 to $< 3 \times \text{ULN}$, ≥ 3 to $< 5 \times \text{ULN}$, ≥ 5 to $< 10 \times \text{ULN}$, ≥ 10 to $< 20 \times \text{ULN}$, and $\geq 20 \times \text{ULN}$ ○ AST: $\leq 1 \times \text{ULN}$, > 1 to $< 3 \times \text{ULN}$, ≥ 3 to $< 5 \times \text{ULN}$, ≥ 5 to $< 10 \times \text{ULN}$, $\geq 10 \times$ to $< 20 \times \text{ULN}$ and $\geq 20 \times \text{ULN}$ ○ Total bilirubin: $\leq 1 \times \text{ULN}$, > 1 to $< 1.5 \times \text{ULN}$, ≥ 1.5 to $< 2 \times \text{ULN}$, $\geq 2 \times \text{ULN}$ ○ ALP: $\leq 1 \times \text{ULN}$, > 1 to $\leq 1.5 \times \text{ULN}$, $> 1.5 \times \text{ULN}$ ● With additional categories: 
 ○ Decreased: post-baseline category $<$ baseline category ○ Increased: post-baseline category $>$ baseline category ○ Same: post-baseline category = baseline category 	
Period 2 (Summary) and Period 3 (Summary for Maintenance Dosing Period Primary Population): Shifts from maximum baseline to maximum post-baseline category

	
Elevated hepatic criteria: maximum ALT $\geq 3 \times \text{ULN}$ and maximum total bilirubin $\geq 2 \times \text{ULN}$ using performing lab reference ranges. Listing of patients who meet any of the following criteria:
 
 ● Elevated hepatic criteria: defined as maximum ALT $\geq 3 \times \text{ULN}$ and maximum total bilirubin $\geq 2 \times \text{ULN}$ ● An ALT or AST $\geq 3 \times \text{ULN}$ ● An ALP $\geq 1.5 \times \text{ULN}$ ● A total bilirubin $\geq 2 \times \text{ULN}$ 	
Period 2 (Fisher’s exact test), Period 3 (Fisher’s exact test for Maintenance Dosing Period Primary Population), Period 4 (Summary): Elevated hepatic criteria
 
Listing: Elevations in hepatic laboratory tests

Special Safety Topic	Definition / Derivation	Analysis / Summary / Listing
	The listing will include: patient demographics, concomitant medications, ALT/AST/ALP/total bilirubin/GGT by visit, treatment start and stop dates, and reason for treatment discontinuation	
	Evaluation of Drug-Induced Serious Hepatotoxicity (eDISH) plot: use maximum ALT measurement and maximum total bilirubin measurement with patients having at least one post-baseline ALT and total bilirubin, which contributes one point to the plot. Patients will be classified into 2 groups: never on ixekizumab or ever on ixekizumab. The measurements do not need to be taken at the same blood draw.	eDISH plot
Cytopenias	
Cytopenias are defined using the PTs from the following 2 sub-SMQs of the Haematopoietic cytopenias SMQ (20000027) as specified in MedDRA:
 
 • Broad and narrow terms in the Haematopoietic leukopenia (20000030) • Broad and narrow terms in the Haematopoietic thrombocytopenia (20000031) 	
Period 2 (Fisher’s exact test), Period 3 (Fisher’s exact test for Maintenance Dosing Period Primary Population): TEAE by PT within sub-SMQ
 
Listing: TEAE

Infections	
Infections are events including all infections (defined using all the MedDRA PTs from the Infections and infestations SOC), serious infections, potential opportunistic infections (OIs), and infections resulting in anti-infective medication administration (i.e., antibacterial, antiviral, antifungal, antiparasitic treatment).
 
Anti-infective medications are defined in the LY2439821 PSAP v8 Appendix 5 (or most current version) including antibiotics, antifungals, antivirals, or antiprotozoals. Listing of patients experiencing a TEAE of infections will be provided including the following additional information: anti-infective medications use (if treated) with medication start/end dates, indication for use, and route; minimum post-baseline value within treatment Period 2 for leukocytes, platelets, lymphocytes, and absolute neutrophils.
	
Period 2 (Fisher’s exact test), Period 3 (Fisher’s exact test for Maintenance Dosing Period Primary Population): SAE by PT, AE leading to treatment discontinuation by PT
 
Listing: TEAE with information collected on Infection eCRF page, TEAE with anti-infective medications.

Special Safety Topic	Definition / Derivation	Analysis / Summary / Listing
	
The list of MedDRA terms used to identify infections that are predefined as potential opportunistic infections (OI) are found in the LY2439821 PSAP v8 Appendix 10 (or most current version). This list contains PTs as contained within categories (narrow and broad) from the Infections and Infestations SOC and the Investigations SOC which can assist in identifying potential OIs. The narrow terms are considered OIs unless medical review determined the reported term is not consistent with the patient’s clinical history/presentation/course. Medical review of broad terms is needed for final determination of patients meeting the program definition of OIs.
 
Listing of patients experiencing a TEAE of OIs will be provided including the following additional information: source of identification (CRF or Lilly specified list), primary/secondary site of infection, primary/secondary infection type, primary/secondary identified by a laboratory diagnostic test (Yes/No), acquired in a Health care setting (Yes/No).
	
Period 2 (Fisher’s exact test), Period 3 (Fisher’s exact test for Maintenance Dosing Period Primary Population): TEAE of OIs by PT
 
Listing: TEAE of OIs.

	
The duration of each common ($\geq 1\%$ of total ixekizumab) TEAE PT of Infections and narrow terms for Opportunistic infections are defined as: Duration of treatment-emergent AE Infections (in weeks) = (End date of AE – Start date of AE + 1) / 7.
 
Only TEAEs of infections beginning during that treatment period will be included in the summary. If a TEAE has not ended by the date of completion of the treatment period, or date of early discontinuation, it will be censored as of that date (last visit within the treatment period, or date of early discontinuation). If a patient has multiple episodes of the same TEAE, the episode with the greatest severity will be used for the duration of event calculation. If a patient has multiple episodes of the same TEAE with the same severity, the episode with the longest duration will be used for the duration of event calculation.
	
Period 2 and Period 3 (Summary): Duration of Common TEAE – Infections

Allergic Reactions/Hypersensitivities	
Allergic reactions/hypersensitivity events will be categorized as either anaphylaxis or non-anaphylaxis events (these will refer to events that are not localized to the site of injection) and summarized separately.
 
Allergic Reactions/Hypersensitivity Events, Anaphylaxis: Anaphylaxis has been broadly defined as “a serious allergic reaction that is rapid in onset and may cause death” (Sampson et al. 2006). Identification of cases of potential anaphylaxis from the clinical trial data involves two screening criteria:
 
1) designed to specifically identify cases (following Criterion 1) based on narrow terms from the MedDRA SMQ for anaphylactic reaction (20000021). Criterion 1 for
	
Period 2 (Fisher’s exact test), Period 3 (Fisher’s exact test for Maintenance Dosing Period Primary Population): TEAE by maximum severity by PT within Category, SAE by PT within Category, AE leading to treatment discontinuation by PT within Category

Special Safety Topic	Definition / Derivation	Analysis / Summary / Listing
	
anaphylaxis is defined by the presence of a TEAE based on the following MedDRA PTs from the anaphylactic reaction SMQ:
 
 • Anaphylactic reaction • Anaphylactic shock • Anaphylactoid reaction • Anaphylactoid shock • Kounis Syndrome • Type 1 hypersensitivity. 
2) to identify possible cases, following Criterion 2 as defined by Sampson et al (2006). Criterion 2 for potential anaphylaxis requires having TEAEs from two or more of four categories of AEs as described by Sampson et al (2006). Occurrence of these events should be nearly coincident; based on recording of events on CRFs. All qualifying events must be within 1 day of study drug injection.
 
The 4 categories to be considered in Criterion 2 are:
 
 • Category A: Involvement of the skin-mucosal tissue • Category B: Respiratory compromise • Category C: Reduced blood pressure or associated symptoms • Category D: Persistent gastrointestinal symptoms 
The specific MedDRA PTs covered by each of these Criterion 2 categories are shown in the LY2439821 PSAP v8 Appendix 6 (or most current version).
 
Summaries of Criterion 2 anaphylactic TEAEs will be provided by the specific combination of categories as follows:
 
 • AB: events based on meeting Category A and Category B (but no other category) • AC: events based on meeting Category A and Category C (but no other category) • AD: events based on meeting Category A and Category D (but no other category) • BC: events based on meeting Category B and Category C (but no other category) • BD: events based on meeting Category B and Category D (but no other category) • CD: events based on meeting Category C and Category D (but no other category) • ABC: events based on meeting Category A, Category B and Category C (but no other category) • ABD: events based on meeting Category A, Category B and Category D (but no other category) 	

Special Safety Topic	Definition / Derivation	Analysis / Summary / Listing
	
 • ACD: events based on meeting Category A, Category C and Category D (but no other category) • BCD: events based on meeting Category B, Category C and Category D (but no other category) • ABCD: events based on meeting each of the 4 Criterion 2 categories 
Summaries of treatment-emergent anaphylactic AEs will be provided for patients meeting each of the 2 criteria and for patients who meet either criteria overall. Severity of treatment-emergent Criterion 2 potential anaphylactic AEs will be based on the maximum severity of the specific events met by the patient. Maximum severity of an (or overall) treatment-emergent potential anaphylactic AE will be based on the maximum severity within Criterion 1 and/or Criterion 2.
 
Allergic Reactions/Hypersensitivity Events, Non-Anaphylaxis: TEAEs of allergic reaction/hypersensitivity categorized as non-anaphylaxis events are defined by the narrow terms within Hypersensitivity SMQ (20000214) excluding the PTs noted in the LY2439821 PSAP v8 Appendix 7 (or most current version) and excluding the anaphylactic events as defined above.
	
	
A by-patient listing will be provided for all patients experiencing TEAE of allergic reactions/hypersensitivities at any time, including status/criterion of anaphylaxis or non-anaphylaxis, and the associated information collected on Allergic / Hypersensitivity Reaction Follow-Up eCRF page if identified by the investigator.
	
Listing: TEAE including information collected on Allergic / Hypersensitivity Reaction Follow-Up eCRF page

Injection Site Reactions	
Injection site reaction is defined using the PTs from the MedDRA HLT of Injection site reactions as specified by MedDRA excluding the following 10 PTs:
 
 1) Embolia cutis medicamentosa 2) Injection site joint discomfort 3) Injection site joint effusion 4) Injection site joint redness 5) Injection site joint infection 6) Injection site joint inflammation 7) Injection site joint movement impairment 8) Injection site joint pain 9) Injection site joint swelling 	
Period 2 (Fisher’s exact test), Period 3 (Fisher’s exact test for Maintenance Dosing Period Primary Population): TEAE by maximum severity by PT
 
TEAE identified by the investigator PT: by maximum severity, by maximum redness category, by maximum hardness category, by maximum swelling category, by maximum pain category

